The following table is a suggestion for dose modifications in subsequent treatment courses:

Dose level	AZA (mg/m ²)	DAC (mg/m ²)
-1	56	15
-2	37	10
-3	18	5

VI. PRETREATMENT AND PER-TREATMENT EVALUATION

Pre-treatment

1. CBC, differential platelet count.

Creatinine, bilirubin, ALT or AST, marrow aspirate with cytogenetics (if bone marrow not done within 1 month and cytogenetics (if previously abnormal) within 3 months.

2. Molecular Diagnostic MDS Panel
3. MDS Flow Panel

During therapy

1. CBC, differential, and platelet count once monthly (the differential may be omitted when the WBC is $< 0.5 \times 10^9/L$.)
2. Creatinine, bilirubin, ALT or AST once monthly.
3. Marrow aspirate to confirm response, to be performed after cycle 2 then every 2 to 4 cycles until response observed, then as clinically indicated
4. Molecular Diagnostic MDS Panel, if previously abnormal, if possible. Not all samples will be collected at all times.
5. Sequential MDS Flow Panel to be performed after cycle 2 then every 2 to 4 cycles until response observed, then as clinically indicated.
6. Conventional cytogenetics to be performed after cycle 2 then every 2 to 4 cycles until response observed, then as clinically indicated.

After Cycle 3

If the study doctor decides it is acceptable, you may be allowed to receive treatment from your local cancer doctor. However, you have to return to Houston at least every 3 months for one year, then every 6 months for your study visits for as long as the patient remains on study.

Supportive care

Supportive measures such as prophylaxis for tumor lysis syndrome, erythropoietin, analgesics, blood transfusions, antimicrobials and hematopoietic colony stimulating factors for treatment of cytopenias are permitted

VII. STUDY END POINTS

Primary:

1. Overall improvement rate (OIR), defined as complete remission (CR), partial remission (PR), marrow CR (mCR), or hematologic improvement (HI), measured at the end of each cycle using each patient's best response with the 2 different agents. Response will be assessed using the modified International Working Group 2006 criteria.¹¹ The best response within the first two cycles will be the OIR for each treatment arm that will be used in the adaptive randomization algorithm.

Secondary:

1. Transfusion independence (defined as being transfusion-free for ≥ 8 consecutive weeks between the first dose and study treatment discontinuation)
2. Cytogenetic response
3. Clinical benefit
4. Duration of response

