The Department of Biostatistics will provide and maintain a website ("Clinical Trial Conduct": <https://biostatistics.mdanderson.org/ClinicalTrialConduct/>) for patients enrolled on this study. The Clinical Trial Conduct website resides on a secure server, and access is gained through usernames and passwords provided to personnel responsible for enrolling patients and updating patient data. The website is accessed through a browser using secure socket layer (SSL) technology. Personnel responsible for enrolling patients on trials, which includes the principal investigator(s), research nurse(s), and data coordinator(s), will be trained by members of the Department of Biostatistics in the use of the trial website; the importance of timely updating of follow-up times and recording of events will be emphasized in training.

XI. Data Safety Monitoring

A data safety monitoring board (DSMB) at MD Anderson will monitor the trial for the safety.

XII. STATISTICAL CONSIDERATIONS

General Description

This is a Phase II open-label, efficacy and toxicity study of two treatment arms (lower doses of Decitabine versus Azacitidine) in subjects with low risk or intermediate-1 myelodysplastic syndrome. Patients will be enrolled to evaluate the 2 agents. In arm A, Decitabine (DAC) will be administered 20mg/m² IV daily for 3 days every 28 days and in treatment B Azacitidine (AZA) will be administered 75mg/m² SC or IV daily for 3 days every 28 days. For both arms, one course will be considered of 4 weeks. An adaptive randomization design will be employed to compare the efficacy between the two arms. The primary efficacy outcome is the overall improvement rate (OIR), defined as complete remission (CR), partial remission (PR), marrow CR (mCR), or hematologic improvement (HI), assessed after maximum of 2 cycles. At the end of the trial, we will estimate the probability that one arm is superior to the other. We will also evaluate toxicity on each arm. A maximum of 120 patients will be accrued, at an expected accrual rate of 3 patients per month.

Study design

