Patients will be assigned to receive Decitabine or Azacitidine, using an adaptive procedure that bases assignment probabilities on observed results in preceding patients. At first, 20 patients will be assigned to each arm with equal probability. As efficacy data accrues, patient assignment to the two arms will become unbalanced in favor of the one that has the higher overall improvement rate (OIR). The OIR for both arms will be estimated with a 95% CI (similar to Bayesian highest posterior density interval).

Based on previous studies, we expect an OIR of about 23% in both arms. Therefore, we assume OIR has a prior Beta distribution (0.46, 1.54) with mean 0.23. Let OIRa and OIRb denote the overall improvement rates for arm A and arm B, respectively. Beginning with the 21st patient in each arm and for each subsequent patient, we will compare OIRa with OIRb, incorporating data from all patients with evaluable response. In order to avoid favoring one arm earlier in a large trial, instead of assigning patients with posterior probability ($P_a = \Pr(\text{OIR}_a > \text{OIR}_b | \text{data})$ and $P_b = 1 - P_a$), we use the following formula to assign patients:

$$A_a = \frac{\sqrt{P_a}}{\sqrt{P_a} + \sqrt{P_b}}, \quad A_b = 1 - A_a, \text{ where } A_a \text{ is the probability of assigning patients to arm A,}$$

A_b is the probability of assigning patients to arm B, P_a is the posterior probability that arm A is superior to arm B and P_b is the posterior probability that arm B is superior to arm A.

If at any point during the trial $\Pr(\text{OIR}_A > \text{OIR}_B | \text{data}) > 0.95$ (or < 0.05) the schedule A (or B) will be selected as superior. If accruing information gives strong evidence that an OIR of 23% or greater is unlikely to be true for any one of the treatment arms ($\Pr(\text{OIR}_A \text{ or } \text{OIR}_B > 0.23 | \text{data}) < 0.05$), assignment to that arm will be stopped. If the maximum of 120 patients is enrolled and evaluated and $\Pr(\text{OIR}_A > \text{OIR}_B | \text{data}) > 0.9$ (or < 0.1), we will declare that arm A (or B) has a higher OIR rate than arm B (or A). Otherwise, the trial will be inconclusive. We used simulation (5,000 simulations per scenario) to evaluate the performance of the adaptive randomization procedure under several different scenarios (Table 2). There was an 86% power to select a superior arm (arm B) if the OIR rates are 20% and 40%, respectively.

Toxicity Monitoring

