Evidence of Toxicity will be monitored closely in all patients. For each arm, treatment will be terminated if $\Pr(\text{non hematological grade 3 or higher Toxicity} > 0.2 | \text{data}) > 0.95$, and the toxicity rate is assumed to follow a non-informative prior of $\text{Beta}(0.4, 1.6)$. Table 1 shows the simulation of the trial. The treatment will be stopped if the number of patients with study drug related toxicities equal to or greater than indicated (i.e., #pts with tox) among the number of patients accrued (i.e., #pts): 4/5, 5/10, 7/15, 8/20, 9/25, 11/30, 12/35, 13/40, 15/45, 16/50, 17/55, 18/60, 19/65, 21/70, 22/75, 23/80, 24/85, 26/90, 27/95, 28/100, 29/105, 30/110, 31/115, 33/120.

Table 1: Operating characteristics of Safety Monitoring (based on 10000 simulations)

True probability	Stop probability	Average sample size
0.15	0.02	117.7
0.2	0.15	108.1
0.25	0.51	83.3
0.3	0.87	53

Table 2: Operating characteristics of adaptive randomization design to compare DAC with AZA. Randomly assign 20 patients to each arm with equal probability before adapting the randomization, tuning parameter of 0.5, and accrual rate of 3 patients/month.

	Arm A	Arm B
OIR Rate	0.05	0.1
Expected # of Patients	20.8	20.9
Pr(Select)	0.03	0.23

Pr(Select Early)	0.01	0.11
Pr(Stop Early)	0.85	0.51
OIR Rate	0.1	0.23
Expected # of Patients	25.5	28.7
Pr(Select)	0.02	0.52
Pr(Select Early)	0.01	0.38
Pr(Stop Early)	0.86	0.13
OIR Rate	0.2	0.4
Expected # of Patients	28.9	35.9
Pr(Select)	0.01	0.86
Pr(Select Early)	0.01	0.81
Pr(Stop Early)	0.85	0.01
OIR Rate	0.23	0.23
Expected # of Patients	44.3	44
Pr(Select)	0.17	0.18
Pr(Select Early)	0.13	0.13
Pr(Stop Early)	0.26	0.24
OIR Rate	0.3	0.5
Expected # of Patients	30.7	38.6
Pr(Select)	0.01	0.85
Pr(Select Early)	0.01	0.81
Pr(Stop Early)	0.81	0.01

Analysis Plan

Data analysis will be performed using SAS or S-plus, as appropriate. All patients will be included in the intent-to-treat analysis for efficacy. Demographic and disease characteristics of the patients at registration will be summarized using descriptive statistics such as mean, standard deviation (SD), median and range. The OIR for both arms will be estimated by Bayesian posterior estimates, along with the 95% credible intervals. The posterior probability that one treatment is better than the other will be computed, and the 95% credible interval of the posterior probability will also be estimated. Time to event end points, such as response duration, overall survival and

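### The plan does not say whether patients lost before a response assessment count in the interim OIR posteriors; if unequal early failures are left out, selection tilts toward the arm losing more

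*Combined protocol and SAP*

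**What the plan says.** Section XII, Study design: from the 21st patient in each arm, the two OIRs are compared before each new assignment, "incorporating data from all patients with evaluable response". The resulting probability that A is better than B feeds the square-root allocation formula. The same probability triggers early selection above 0.95 "or < 0.05) the schedule A (or B) will be selected as superior", and it decides the final call at 120 patients (0.9 or 0.1). The futility rule closes an arm when Pr(OIR > 0.23) falls below 0.05. These rules condition on data and name no population.

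Section XII, Analysis Plan: "All patients will be included in the intent-to-treat analysis for efficacy".

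On the outcome, Section VII, Study End Points, says "The best response within the first two cycles will be the OIR for each treatment arm that will be used in the adaptive randomization algorithm", and the General Description says OIR is "assessed after maximum of 2 cycles".

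Nothing defines *evaluable*, says how a patient without an assessment is scored, or gives a loss rate. The withdrawal criteria foresee losses through withdrawn consent, progression, intercurrent illness and toxicity. The toxicity boundary, by contrast, states its denominator as the number accrued.

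**The concern.** Two populations are named for the same endpoint, and neither comes with a scoring rule. If a patient who dies or stops in cycle 1 is treated as not evaluable, that failure leaves the denominator and the arm's observed OIR rises. If the arms lose patients at different rates, the comparison is distorted.

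The interim dataset usually settles this trial. In Table 2, at 20% versus 40%, 0.81 of the 0.86 probability of selecting arm B comes from early selection. The trial could therefore stop for an arm that would not meet the rule on all randomised patients. The study is open-label, so without a written rule the staff entering outcomes could decide case by case, knowing the arm.

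**Working it through.** **Inputs from Section XII.** Prior: "we assume OIR has a prior Beta distribution (0.46, 1.54) with mean 0.23", used for each arm. Run-in: "At first, 20 patients will be assigned to each arm with equal probability". Table 2 settings: "tuning parameter of 0.5, and accrual rate of 3 patients/month". Maximum 120 patients; outcome at two 28-day courses (56 days). Loss rates are assumptions, because the documents give none.

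**1. Reproducing the plan with no loss.** The design was simulated with 3,000-5,000 runs per scenario (Monte Carlo SE about 0.005-0.008). The text allows more than one reading of the stopping rules.
- Reading (a): a futile arm closes and the other continues. Power at 20% versus 40% is 0.895.
- Reading (b): accrual ends when either arm meets a rule, and an early selection stands. Power is 0.885.
- Reading (c): as (b), but the winner is judged at 0.9/0.1 once pending outcomes are in. Power is 0.863, against the stated 86%. Expected numbers are 28.3/35.1, against 28.9/35.9.

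Reading (c) reproduces the power. At 23% versus 23% it selects A/B with probability 0.158/0.160, against Table 2's 0.17/0.18.

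**2. Excluding early failures, true OIR 23% in both arms.** If a share L of an arm is lost, all non-responders, and excluded, the observed rate is 0.23/(1 − L). For L = 0.10 this is 0.23/0.90 = 0.256. Each cell gives Pr(select arm losing more) / Pr(select other arm):

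| Loss (assumed) | Reading (c) | Reading (a) |
|---|---|---|
| 0% / 0% | 0.154 / 0.160 | 0.195 / 0.202 |
| 10% / 10% | 0.164 / 0.167 | 0.198 / 0.198 |
| 10% / 0% | 0.222 / 0.114 | 0.271 / 0.141 |
| 20% / 5% | 0.282 / 0.089 | 0.330 / 0.108 |
| 20% / 0% | 0.332 / 0.067 | 0.383 / 0.086 |

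Two separately coded versions, each with a no-loss value of 0.20 for the arm losing more, gave 0.27 and 0.29 at 10% versus 0%. One of them gave 0.23 at 5% versus 0%. Counting the lost patients as non-responders returns reading (c) to 0.154/0.160 at 20% versus 5%.

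**3. A case that can be checked directly.** The posterior is Beta(0.46 + x, 1.54 + n − x).
- Selection: A 5/25 gives Beta(5.46, 21.54) and B 10/25 gives Beta(10.46, 16.54). Pr(B > A) = 0.938, so no selection. Excluding two early failures in B gives 10/23, Beta(10.46, 14.54), and 0.959. B is now selected.
- Futility: 3/30 gives Pr(OIR > 0.23) = 0.028 and the arm closes. With six failures excluded, 3/24 gives 0.085 and it stays open.

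**4. Futility.** With 10% loss in both arms at 23%/23%, closure per arm under reading (c) falls from 0.116/0.104 to 0.068/0.062. With A truly at 15% and B at 23%, closure of A falls from 0.35 to 0.20 if 20% of A are excluded failures.

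**5. Allocation.** With 7/24 against 7/30, P_a is about 0.68, so A_a = √0.68/(√0.68 + √0.32) = 0.593 instead of 0.5. Over the whole trial the effect is small: at 20% versus 5% loss, expected numbers are 48.8/44.7, against 45.4/45.2 with no loss.

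**6. Power at 20% (A) versus 40% (B).** It is 0.87 with no loss, 0.75 if A loses 20% and B 5%, and 0.95 if A loses 5% and B 20%.

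**7. Loss unrelated to response, 20% in A and 5% in B, with 23% among evaluable patients in both arms.** The evaluable-only rule gives 0.147/0.154, so no bias. Counting the lost as failures gives 0.076/0.233, against the arm losing more.

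**The case against.** A reader might infer that the plan removes early failures from its decisions, that its intent-to-treat analysis scores the same patients as non-responders, and that the arm losing more is therefore favoured. The documents do not support that much.

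- The comparison is repeated for each new patient, when many earlier two-course outcomes are still pending. In that setting *evaluable* can simply mean that the outcome is known. No section says early failures are excluded.
- The Analysis Plan includes everyone but does not say how an unassessed patient is scored. Non-responder scoring is the usual convention, not a stated rule.
- The quoted phrase sits in the allocation comparison. Its reach to selection, futility and the final rule is inferred from the shared posterior and the unnamed data.
- Response is measured at the end of each cycle and blood counts are monthly, so a patient who stops in cycle 2 may already have an assessment. The unassessed group is smaller than all those who stop before two courses.
- Large losses are not documented. The earlier decitabine trial in the Rationale had about 70% alive at 500 days. Under a constant hazard that implies 1 − 0.7^(56/500) = 3.9% dead by day 56. Withdrawals would add to this, but nothing shows that the arms differ.
- Equal loss is symmetric for selection, and loss unrelated to response causes no bias under an evaluable-only rule.

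All of this stands, and it limits the point to a conditional one. It does not remove it: even if *evaluable* means no longer pending, the plan still does not say whether a death in cycle 1 is a non-response or is left out.

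**Conclusion.** The plan should be changed, for a conditional reason. The population for the interim posteriors is undefined, it is worded differently from that of the efficacy analysis, and unassessed patients have no scoring rule. If early failures are left out, and losses are unequal and mainly non-responders, early selection is biased toward the arm that loses more. At an assumed 10% versus 0%, and 23% in both arms, its selection probability rises from about 0.16-0.20 to 0.22-0.29. At 5% versus 0% the rise is about 0.20 to 0.23. Equal 10% loss roughly cuts the chance of futility closure from 0.11 to 0.065 per arm. Allocation is little affected, and the toxicity rule not at all, since it counts patients accrued. The 86% power is not contradicted: it reproduces on its own inputs with no loss. All loss rates here are assumptions.

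**What to change.** In Section XII, Study design, replace the phrase on evaluable response with: *incorporating all randomised patients whose two-course assessment date has passed; the best documented response within two courses counts, and patients with no documented response, including those who died or stopped treatment earlier, count as non-responders.*

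Every patient should enter at the same two-course time point. If failures entered on the day they occurred while responders waited, interim rates would be temporarily too low. State that this one set serves allocation, early selection, futility and the final posterior. Rerun Table 2 with a stated loss rate.

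The cost is one sentence, a data-entry rule on the trial website and a rerun of the simulations. Observed OIRs become slightly lower. Loss unrelated to response will count against the arm that loses more (step 7 of the working), so report an evaluable-only posterior as a sensitivity analysis.

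### Table 2 of section XII does not describe the stopping rules as written: under those rules, two of its expected sample sizes are too small for its own stop and selection probabilities

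*Combined protocol and SAP*

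**What the plan says.** Section XII, Study design, gives three decision rules on the overall improvement rate (OIR).

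- Selection: an arm is chosen if the posterior probability that it is better exceeds 0.95, at any time.
- Futility: an arm is closed if its posterior probability of an OIR above 0.23 falls below 0.05.
- Final: a cut-off of 0.90 applies at full enrolment.

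The last two adjoin in the text: "assignment to that arm will be stopped. If the maximum of 120 patients is enrolled and evaluated". Nothing says that closing one arm ends the trial, or that 0.90 may be used before 120.

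The caption of Table 2 (the operating characteristics table) sets the burn-in: "Randomly assign 20 patients to each arm with equal probability before adapting the randomization". For the scenario 0.05/0.10 the table prints, for arms A and B, "Expected # of Patients 20.8 20.9", "Pr(Select) 0.03 0.23", "Pr(Select Early) 0.01 0.11" and "Pr(Stop Early) 0.85 0.51". For 0.10/0.23 it prints "Expected # of Patients 25.5 28.7" and "Pr(Stop Early) 0.86 0.13", with early selection 0.01 and 0.38. The row labels are not defined.

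**The concern.** Table 2 is the plan's only evidence on how often the design names a winner when the arms are equal, and how often it finds the better arm. If its figures come from a different rule, the stated power, false-selection rate and expected size belong to another design.

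The sign of trouble is in the low-response rows. Many trials there appear to end neither by early selection nor by closure of both arms, so they should run to 120. Yet the mean total at 0.05/0.10 is barely above the 40-patient burn-in.

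**Working it through.** **Printed totals.** 20.8 + 20.9 = 41.7 at 0.05/0.10, and 25.5 + 28.7 = 54.2 at 0.10/0.23.

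**Bound 1: the other arm continues after a closure.** A trial then ends before 120 only by early selection or by closure of both arms. Closure of both cannot be more frequent than closure of arm B, so

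share reaching 120 ≥ 1 − Stop Early(B) − Select Early(A) − Select Early(B), and mean total ≥ 120 × that share.

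- 0.05/0.10: 1 − 0.51 − 0.01 − 0.11 = 0.37; 120 × 0.37 = 44.4, against 41.7.
- 0.10/0.23: 1 − 0.13 − 0.01 − 0.38 = 0.48; 120 × 0.48 = 57.6, against 54.2.
- Worst-case rounding (three cells, 0.005 each): 120 × 0.355 = 42.6 and 120 × 0.465 = 55.8, still above the printed totals.

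This floor lets every other trial enrol nobody. If each trial completes the burn-in, it rises to 40 + 80 × 0.37 = 69.6 and 40 + 80 × 0.48 = 78.4. If the Stop Early row also counts an arm dropped because the other was selected, the shares become 0.38 and 0.49 and the floors 45.6 and 58.8. Simulation error is no explanation, because cells and means should come from the same runs. The other three rows do not breach the bound: 20.4 against 64.8, 60.0 against 88.3, and 20.4 against 69.3.

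**Bound 2: the first closure ends the trial.** Take early as before 120. At 0.05/0.10 the non-early selections are (0.03 − 0.01) + (0.23 − 0.11) = 0.14, which the text allows only at 120. With the burn-in, mean total ≥ 40 + 80 × 0.14 = 51.2; with four cells each off by 0.005, 40 + 80 × 0.12 = 49.6. The table has 41.7. No other row breaches this bound; at 0.10/0.23 it is 40 + 80 × 0.15 = 52.0 against 54.2.

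**Simulation.** Inputs from the plan: Beta(0.46, 1.54) priors, 20 per arm before adapting, square-root allocation, maximum 120. Assumed: a response lag of 6 patients (2 months × 3 per month), looks from patient 41, and early selection ending accrual. There were 30,000 trials per cell (60,000 where the first closure ends the trial); standard error at most 0.003. In the first simulated column the closed arm is still compared, at every look or only at 120, which gives the ranges. The last column comes from smaller independent runs.

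| Quantity | Table 2 | Other arm continues | First closure ends trial, 0.90 only at 120 | First closure ends trial, 0.90 applied then |
|---|---|---|---|---|
| False selection, 23%/23% | 35% | about 40% | 29% | about 36% |
| Mean total, 23%/23% | 88.3 | 95 to 100 | 89 | about 89 |
| Select B, 0.05/0.10 | 0.23 | – | 0.12 | 0.25 to 0.29 |
| Select B, 0.10/0.23 | 0.52 | 0.66 to 0.68 | 0.40 | 0.54 to 0.57 |
| Select B, 0.20/0.40 | 0.86 | 0.90 | 0.88 | 0.89 to 0.90 |

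With the other arm continuing and the comparison made at every look, mean totals in the two low-response rows are 46.9 and 65.4. Arm B closes for futility at 0.05/0.10 in 81% to 87% of trials, against 51% printed. Independent runs of that reading with lags of 0, 6 and 12 patients gave 45.0 to 48.4 and about 65 to 66.

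If the first closure ends the trial, the mean totals by row are 41.3, 53.4, 62.8, 89.3 and 66.4, against 41.7, 54.2, 64.8, 88.3 and 69.3. Futility closure plus being dropped on the other arm's early selection then matches all ten Stop Early cells within 0.022.

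**The case against.** The strongest reply is that the sample sizes are not miscalculated. They look right for a program in which the first closure ends the trial and 0.90 is applied at that moment, and what is missing is a sentence in the text. That reading also reproduces the 35% false selection at 23%/23%, the plan's own expected scenario. This largely stands. A reader might infer a plain arithmetic slip in Table 2, and the documents do not show one. But the rule that fits is inferred, the fit is only approximate, and applying 0.90 before 120 contradicts the text.

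Bound 2 depends on an undefined label. If early means selection by the 0.95 rule and the remainder means 0.90 at whatever point the trial ends, no bound is breached. The conflict with the text over when 0.90 applies remains.

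A reader might also infer that power could be far below 86%. Simulated values of 0.75 and 0.56 arise only if a closed arm is never compared again and futility looks start at patient 1. The documents do not support that. The General Description promises an end-of-trial probability of superiority, the rule at 120 exempts no closed arm, and the Analysis Plan includes all patients.

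Nor are 44.4 and 57.6 absolute minima of the written rules. Looks from patient 1 give simulated means as low as 27.9 and 42.5, but arm B's stop rate at 0.05/0.10 is then at least 0.85, not 0.51.

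Finally, the two rows breaching Bound 1 are low-response scenarios, the version status shows entry closed, and the final posterior comparison does not use Table 2. This limits the consequences but does not remove the inconsistency.

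**Conclusion.** The inconsistency holds. If the other arm continues, two of the five rows break a bound built from their own cells, even with worst-case rounding. If the first closure ends the trial, the 0.05/0.10 row conflicts with the written timing of the 0.90 cut-off, given the burn-in and early read as before 120.

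Under the written wording (other arm continues, closed arm still compared, looks from patient 41, early selection ending accrual, 6-patient lag), false selection at 23%/23% is about 40% rather than 35%, and the mean total is about 95 to 100 rather than 88. Selection of B at 0.10/0.23 is about 66% to 68% rather than 52%. Power at 0.20/0.40 is about 0.90, so the quoted 86% is not shown to be overstated. The size of these shifts depends on the listed assumptions; Bound 1 needs only the printed cells and Stop Early read as above.

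This should be fixed, because Table 2 governs how much weight a declared winner deserves.

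**What to change.** Reconcile the Study design text with Table 2. State:

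1. What closing one arm does to the trial and to the comparison: whether the trial ends or the other arm continues, and how the closed arm is then compared.
2. When the 0.90 cut-off applies, and whether early selection ends accrual.
3. From which patient the selection looks and the futility looks start. The text allows selection at any time, ties the comparison to the 21st patient in each arm, and gives futility no start. With the stated prior, 0 responders in 6 already meets the futility rule (posterior probability 0.045).

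Then define Table 2's row labels, rerun it under that wording, and restate power, false selection and expected sample size, including at 23%/23%.

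The cost is wording and one simulation rerun. The maximum of 120 is unchanged. Some stated figures may become less favourable. With entry closed, the rerun bears on how the final comparison is read, not on accrual.

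### The toxicity rule applies to each arm, but Table 1's stop probabilities are those of a single group of 120, the maximum for both arms together

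*Combined protocol and SAP*

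**What the plan says.** Section XII, Toxicity Monitoring, states the scope of the rule: "For each arm, treatment will be terminated if" the posterior probability of a toxicity rate above 0.2 is more than 0.95, with a Beta(0.4, 1.6) prior. It then lists 24 stopping counts, one for every 5 patients, from 4/5 to 33/120.

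On performance it says "Table 1 shows the simulation of the trial". Table 1 (the safety table in Section XII, not the prognostic table at the end) has four rows, starting with "0.15 0.02 117.7" (true rate, stop probability, average size) and ending with 0.87 and 53 at a true rate of 0.3. It gives neither its N nor its look schedule. On frequency the text says only "Evidence of Toxicity will be monitored closely in all patients".

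On size, the General Description says "A maximum of 120 patients will be accrued" for the two-arm trial, and Study design says "At first, 20 patients will be assigned to each arm with equal probability". Table 2 gives mean arm sizes from 20.8 to 44.3.

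**The concern.** An average size of 117.7 cannot describe one arm of a two-arm trial capped at 120 in total, unless the other arm is almost empty. If Table 1 was computed for 120 patients in one group, its stop probabilities do not apply to a rule that looks at each arm separately, because an arm with fewer patients is checked fewer times.

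Table 1 is the only place where the protocol says how reliably the safety rule stops a toxic arm. A DSMB member or ethics reviewer would read from it that an arm with 30% toxicity escapes the rule 13% of the time.

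Two smaller matters arise in the same paragraph. Some listed counts do not follow from the stated posterior rule. The toxicity event is also described in two ways: the rule counts non-haematological events of grade 3 or above, while the sentence introducing the list refers to toxicity related to study drug.

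**Working it through.** **Inputs.** All from Section XII: prior Beta(0.4, 1.6), threshold 0.2, cutoff 0.95, the 24 listed counts, a maximum of 120 over two arms, and Table 1 (10,000 simulations).

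**Method.** Exact binomial recursion. Let f_n(x) be the probability of x toxicities after n patients with no earlier stop:

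f_n(x) = (1 − p) f_{n−1}(x) + p f_{n−1}(x − 1).

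At a look with stopping count b_n, the stop probability is s_n = Σ_{x ≥ b_n} f_n(x), and those states are then removed. The total stop probability is Σ s_n. The average size is Σ n s_n + N(1 − Σ s_n).

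**Step 1: reproduce Table 1.** One group, N = 120, listed counts, looks every 5 patients:

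| True rate | Stop, exact | Stop, Table 1 | Average N, exact | Average N, Table 1 |
|---|---|---|---|---|
| 0.15 | 0.024 | 0.02 | 117.7 | 117.7 |
| 0.20 | 0.151 | 0.15 | 108.1 | 108.1 |
| 0.25 | 0.517 | 0.51 | 83.3 | 83.3 |
| 0.30 | 0.872 | 0.87 | 53.0 | 53 |

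The simulation standard error at 0.25 is √(0.517 × 0.483 / 10,000) = 0.005, so 0.517 against 0.51 is within simulation error. Not counting the look at 120 as a stop gives 0.513 at 0.25 and 0.867 at 0.30.

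**Step 2: try other readings.**
- Looks after every patient from n = 5, N = 120, true 30%: stop 0.906, average size 43.8. This does not fit 0.87 and 53.
- Two separate arms of 60, at least one stopping, listed counts: 1 − (1 − 0.1148)² = 0.217, 1 − (1 − 0.3473)² = 0.574 and 1 − (1 − 0.6549)² = 0.881 at 20%, 25% and 30%, against 0.15, 0.51 and 0.87. With both arms fixed at 60, the total average size at 30% is 2 × 39.3 = 78.6, against 53.

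**Step 3: per-arm stop probability.** In each cell the first figure uses the listed counts every 5 patients; the second uses the stated rule after every patient from n = 5.

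| Arm size | True 20% | True 25% | True 30% |
|---|---|---|---|
| 20 | 0.056–0.102 | 0.143–0.219 | 0.282–0.378 |
| 40 | 0.096–0.146 | 0.269–0.343 | 0.518–0.589 |
| 60 | 0.115–0.171 | 0.347–0.426 | 0.655–0.717 |
| 100 | 0.141–0.203 | 0.464–0.548 | 0.817–0.864 |
| Table 1 | 0.15 | 0.51 | 0.87 |

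Checking from the first patient (the rule is already met at 2/2, posterior 0.957) gives 0.727 for N = 60 at 30%. The share of 60-patient arms at 30% with no toxicity stop is 1 − 0.717 = 0.283 to 1 − 0.655 = 0.345, against 1 − 0.87 = 0.13. For a 60-patient arm to stop with probability 0.87, the true rate must be 0.337 (every patient) to 0.347 (listed counts).

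**Step 4: the listed counts.** The rule stops at the smallest x for which the upper tail of Beta(0.4 + x, 1.6 + n − x) beyond 0.2 exceeds 0.95.

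| n | Listed count | Count under the rule | Posterior at that count |
|---|---|---|---|
| 45 | 15 | 14 | 0.9531 |
| 70 | 21 | 20 | 0.9502 |
| 90 | 26 | 25 | 0.9564 |
| 95 | 27 | 26 | 0.9524 |
| 120 | 33 | 32 | 0.9564 |

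The other 19 agree. The first two discrepancies lie in "13/40, 15/45, 16/50" and "19/65, 21/70, 22/75". No single cutoff with a fixed 0.2 explains the list, since 19/65 (0.9557) stops while 25/90 and 32/120 (0.9564 each) do not. Replacing the fixed 0.2 by a Beta(200, 800) reference reproduces all 24 counts; Beta(100, 400) misses 4 and Beta(400, 1600) misses 3. The protocol states no such reference. Correcting the five counts moves the stop probability at N = 60 from 0.655 to 0.664 at true 30%, and from 0.115 to 0.120 at true 20%.

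**The case against.** The strongest reply is that Table 1 is numerically right for what it describes. It can be read as toxicity pooled over the whole trial, and the sentence calling it a simulation of the trial, together with a list that runs to 120, supports that. But the pooled reading is the same single group of 120, and it contradicts the explicit per-arm rule. It explains where the figures came from without making them apply.

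Second, the protocol fixes no arm size of 60. That is true: 60 is an even split with no efficacy or futility stop, and adaptive randomisation or closure of one arm could make the other larger. An arm of 100 is what remains if the other keeps only its first 20, and somewhat more is possible if the other closes for toxicity before that. At 100 the figure for 30% is still 0.82 to 0.86. At true 25%, a 100-patient arm checked after every patient (0.548) does pass Table 1's 0.51. Table 2's smaller sizes are means after early stopping, not caps.

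Third, patient protection is unchanged. The stopping count at a given n is the same whatever the cap, a 60-patient arm at 30% treats 39.3 patients on average (listed counts) against 53 in Table 1, and a DSMB also watches safety. All this stands. It limits the defect to the stated operating characteristics.

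Finally, the five counts differ by one each, 20/70 is nearly a tie, and only the count at 45 falls within a 60-patient arm. The Beta(200, 800) match is a back-calculation and does not prove how the list was made.

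**Conclusion.** The concern holds. Table 1 matches one group of 120 checked every 5 patients, while the rule works on each arm of a trial whose two arms share 120. For an arm of 60 with true 30% toxicity, the stop probability is 0.65 to 0.72 rather than 0.87; at 25% it is 0.35 to 0.43 rather than 0.51. Smaller arms do worse, and at 30% Table 1's value is approached only by an arm of about 100 or more.

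These figures assume independent patients with a constant toxicity rate, toxicity known at each look, and no efficacy or futility stop. An arm that ends early for those reasons has fewer chances to stop for toxicity but also exposes fewer patients.

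The five stopping counts do conflict with the written rule, with a small effect. The two event descriptions are a wording point. This should be corrected, but it does not undermine the stopping boundary itself.

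**What to change.** Replace Table 1 with per-arm operating characteristics at attainable sizes, for example 20, 40, 60 and 100, and state N and the look schedule. If arm sizes are instead simulated with efficacy and futility stopping, report toxicity stops separately.

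For the five counts, either keep the list and state the reference distribution that produced it, if the sponsor can confirm one (Beta(200, 800) would fit), or change them to 14/45, 20/70, 25/90, 26/95 and 32/120. Use one event definition in both sentences.

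The cost is a short recalculation and some wording. Keeping the listed counts leaves conduct unchanged, though the published stop probabilities become less favourable. Correcting them raises the chance of stopping an acceptable arm only slightly (Step 4). The cover information shows the study closed to new entry, so the correction now mainly serves accurate reporting of how the safety monitoring performed.
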